6.4.1. Missing Dates

Partial or missing dates will be imputed only if a date is required to derive a study endpoint (eg, time to failure, duration of AE) or a variable used in study analyses. Otherwise no date imputation will be done. Date imputation will follow the rules below.

Efficacy Related Dates

Partial or missing dates required to compute efficacy endpoints will be imputed as follows:

- Missing day only: For partial dates with only the day of the month missing, the day will be imputed as the 15th day of the month, provided that a preceding date of interest does not occur in the same month. If the preceding date does occur in the same month, then the missing day will be imputed as half the distance between the preceding date and the end of the month. For example, if the Week 2 visit occurs on the 15th day and Week 3 day was missing, Week 3 day could not be day 15, it would be day 22.
- Missing month and day: For partial dates with the month and day missing, the month and day will be imputed as July 1st, provided that a preceding date of interest does not occur in the same year. If the preceding date occurs in the same year, then the month and day will be imputed as half the distance from the preceding date to the end of the known year.
- Missing month, day, and year: Missing dates will be imputed as the date of first dose.
- In situations where the above rules result in an illogical time (eg, negative study day, negative time to failure, etc) the date will be imputed as the date half the distance between the preceding date of interest and the partial date.

Safety Related Dates

For medications occurring prior to first dose of study drug. Missing or partial date will not be imputed. For safety data besides medications where the date of onset is during or after administration of the first dose of study drug, missing or partial start dates will be imputed as the earliest possible date that is on or after the date of the first dose of study drug. For events occurring prior to first dose of study drug, missing or partial dates will not be imputed.

- Missing day only: If the start date and date of first dose share the same month and year, the missing start day will be imputed as the day of first dose. If the start date month is after the month of first dose, day will be imputed as the 1st (ie, 01-Jan-2019).

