- Missing month only: If the start date and date of first dose share the same year, month will be imputed as the month of the first dose. If the start date year is after the year of the first dose, the month will be imputed as Jan.
- Missing month and day: If the start date and date of first dose share the same year, day and month will be imputed as the day and month of first dose. If the start date year is after the year of first dose, the month and day will be imputed as January 1st (ie, 01-Jan-2019).

- Missing month, day, and year: Missing start dates will be imputed as the date of first dose.
- For partial end dates: Missing month and day: if year matches the year of the last date of study (date of last contact if subject lost to follow-up; date of completion or early termination), then impute as the month and day of the last date of the study, otherwise assign 31-December.
- Missing month only: if year matches the year of the last date in the study (date of last contact if subject lost to follow-up; date of completion or early termination), then impute as the month of the last date of the study, otherwise assigned December.
- Missing day only: if the month and year match the month and year of the last date of study, then impute as the day of the last date of the study; otherwise assign the last day of the month.

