11.1. Adverse Events

Per the study protocol all adverse events (AE) occurring during the study, whether or not attributable to study drug, will be recorded in the subject’s source documents and CRF. The adverse event reporting period will start at the date of informed consent and continue through the end of the study (Week 24 visit). Treatment emergent adverse events (TEAE) are defined in Section 4.2.1.

AE severity will be assessed by the Investigator as mild, moderate or severe. The Investigator will also assess the relationship of each AE to study drug (none, unlikely, possible, probable, definite). Treatment-related AEs are defined as events the Investigator considers to be possibly, probably, or definitely related to study drug, as well as events with “unknown” relationship.

Adverse event summaries will present data for the 3 treatment arms. An overall summary of adverse events will be provided that reports, for each treatment arm, both the number (%) of events meeting a specific criterion and the number (%) of subjects with at least one event meeting that criterion during the AE reporting period. Events meeting the following specific criteria will be presented in this table:

- Any reported adverse event (ie, both pre-existing and treatment-emergent events)
- For treatment-emergent AEs:
 - Any TEAE
 - Any serious TEAE
 - Any related serious TEAE
 - TEAEs by severity (mild, moderate, severe)
 - TEAEs by relationship (none, unlikely, possible, probable, definite)
 - TEAEs by relationship (not related, related)
 - TEAEs by action taken with study drug (dose not changed, dose reduced, dose interrupted, drug withdrawn, not applicable, unknown)
 - TEAEs by outcome (Fatal, Not recovered/Not resolved, Recovered/Resolved, Recovered/Resolved with sequelae, Recovering/Resolving)

Three overall summary tables will be provided, as follows:

- all AEs during the study
- all AEs occurring after Week 6 on the study, defined as AEs with start date after the date of the Week 7 Day 1 dose.
- All AEs occurring after Week 6 of the study defined as AEs with start date after the date of the Week 7 Day 1 dose, or AEs that are ongoing (ie, not resolved) on the date of the Week 7 Day 1 dose.

Dosing dates will be obtained from subject treatment diaries.

In addition to the overall summaries described above, the following summaries of TEAEs occurring anytime during the study will be produced:

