- Incidence by SOC and preferred term (PT), in alphabetical order of SOC and PT, for both all TEAE and related TEAE
- Incidence by PT, in decreasing frequency of PT, for both all TEAE and related TEAE
- Incidence of TEAEs that resulted in dose reduction or discontinuation of study drug (ie, action taken with study drug reported as dose reduced, dose interrupted, or drug withdrawn), in decreasing frequency of PT
- Incidence of TEAE by PT and severity (mild, moderate, severe), in alphabetical order of PT

- Incidence of TEAE by PT and relationship (related, not related), in alphabetical order of PT
- Incidence of TEAE by PT for events of special interest: COVID-19

The following summaries will also be produced of TEAEs occurring after Week 6 (occurring after Week 6 or ongoing after Week 6) on the study (see definitions above):

- Incidence by SOC and PT, in alphabetical order of SOC and PT
- Incidence by PT, in decreasing frequency of PT
- Incidence of TEAEs that resulted in dose reduction or discontinuation of study drug (ie, action taken with study drug reported as dose reduced, dose interrupted, or drug withdrawn), in decreasing frequency of PT

The following will also be summarized:

- Incidence of TEAEs that occurred from Week 6 (approximately Study Day 42) visit + 1 day through Week 7 visit (approximately Study Day 49) will be assessed for any possible withdrawal effects when switching to placebo during the first Week 7 timeframe for the cytisinicline 6 weeks arm.
- Incidence of TEAEs by time of onset (Up to Week 6 [approximately Study Day 42] visit and after Week 6 visit through Last Dose)
- Incidence of TEAEs by primary endpoint status

In summaries of AE incidence, if a subject experiences the same AE (preferred term) multiple times that subject will be counted only once for that preferred term. Similarly, if a subject experiences multiple AEs (preferred terms) within the same SOC then that subject will be counted only once for that SOC. When summarizing by severity and relationship, only the AE with the highest severity or relationship will be counted.

A Kaplan-Meier figure of time to first TEAE (ie, time from date of randomization to earliest TEAE start date) will be provided by treatment arm. Subjects with no Adverse events will be censored at their last visit.

In addition to summary tables, the following listings will be produced.

- All AEs

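### Setting partial AE start dates to the earliest possible date suits the treatment-emergent flag but not the tables split at the Week 6 switch, and the rule for a missing month can give dates before first dose

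*SAP*

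**What the plan says.** For AEs with onset once dosing has begun, SAP 6.4.1 (Safety Related Dates) sets a governing rule: "missing or partial start dates will be imputed as the earliest possible date that is on or after the date of the first dose". The detailed rules for AE dates are:

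- Start, day missing: the day of first dose if the month and year match first dose; otherwise "If the start date month is after the month of first dose, day will be imputed as the 1st".
- Start, month missing: "If the start date and date of first dose share the same year, month will be imputed as the month of the first dose". The known day is kept.
- Start, month and day missing: "If the start date and date of first dose share the same year, day and month will be imputed as the day and month of" that dose.
- Start, whole date missing: "Missing start dates will be imputed as the date of first dose".
- End, day missing: the last study day if the month and year match it; "otherwise assign the last day of the month".

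Safety objective 2 (SAP 3.4) compares Arms B and C on AEs after Week 6. SAP 11.1 uses AE dates around that boundary in four ways:

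- an overview of after-Week-6 AEs, "defined as AEs with start date after the date of the Week 7 Day 1 dose";
- a second overview that adds AEs still unresolved on that date. The after-Week-6 tables by system organ class and preferred term are described in the same occurring-or-ongoing way;
- a window meant to show possible withdrawal effects in Arm B: "Incidence of TEAEs that occurred from Week 6 (approximately Study Day 42) visit + 1 day through Week 7 visit";
- a table by time of onset, up to Week 6 or after it through last dose.

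The date rules mention neither the Week 6 switch nor the visit at which an AE was reported. The back-up CRF question in SAP 4.2.1.1 concerns only the first dose.

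**The concern.** One imputation rule serves two boundaries that call for different directions. At first dose, the earliest date errs toward calling an AE treatment-emergent. At the Week 6 switch, the same choice credits a post-switch onset to the period when both active arms were still on cytisinicline. At stake is the descriptive picture of what six more weeks of drug adds in Arm C, and of what stopping does in Arm B.

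End dates are pushed the other way, to the latest date, so the ongoing component of the second definition can pick up AEs that were already over. Separately, the missing-month rule does not follow its own governing sentence, because keeping the known day while borrowing the first-dose month does not guarantee a date on or after first dose.

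**Working it through.** The documents state no figure to reproduce here. The inputs are the SAP 6.4.1 rules and the SAP 11.1 boundaries, with Week 7 Day 1 taken as Day 43. Two assumptions are mine: first dose equally likely on each of 365 dates, and onset (or end) equally likely on each day of the stated range. L is the length of a calendar month in days.

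**1. Start-date-only tables, day missing.** Day 43 is 42 days after first dose, so it always falls in a later calendar month. A post-switch AE is lost when its month is the month of Day 43, because the 1st of that month is on or before Day 43. Summed over first-dose dates, the days left in the month after Day 43 are Σ L(L−1)/2 = 7×465 + 4×435 + 378 = 5,373.

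- Days 44-84: 5,373 / (365×41) = 5,373 / 14,965 = 36%.
- Days 44-168: 5,373 / (365×125) = 5,373 / 45,625 = 12%.
- By week of onset: Week 7 88%, Week 8 67%, Week 9 44%, Week 10 21%, Week 11 2%, then 0%.

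The first range fits the onset-period table, which stops at last dose. The second fits the overview, which runs to Week 24. No pre-switch event moves the other way. If a share q of AEs lacks the day, the loss is 0.36q or 0.12q. At q = 5-10% that is 1.8-3.6% or 0.6-1.2%.

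Example: first dose 1 March, Week 7 Day 1 on 12 April, true onset 15 April. The imputed start is 1 April (Day 32), so the AE is lost.

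**2. Start-date-only tables, more missing.** With month and day missing, 94% (Days 44-84) and 83% (Days 44-168) move to Day 43 or earlier. With the whole date missing, all do.

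**3. Week 7 window (Days 43-49), day missing.** There are 7×365 = 2,555 true date pairs. An AE stays in only if the 1st of its month also falls in the window, which gives 12×(7+6+5+4+3+2+1) = 336 pairs. So 336/2,555 = 13% stay and 87% leave. For each month, 7 first-dose dates place its 1st inside the window, and all L onset days of that month are sent there. The imputed total is 7×365 = 2,555, of which 2,219 (87%) come from outside. The net ratio is 1.00.

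Example of entry: first dose 20 March, Week 7 Day 1 on 1 May, true onset 25 May (Day 67). The imputed start is 1 May (Day 43).

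A net loss needs clustering or more missing information. If the daily rate in Week 7 were double that elsewhere, the window would hold (2×0.132 + 0.868)/2 = 57% of its true count. With month and day missing, the net ratio is 0.11 (onset to Day 86) or 0.34 (to Day 168). With the whole date missing it is 0.

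**4. Occurring-or-ongoing tables.** An AE that truly began after Day 43 also ends after Day 43. Given an earlier imputed start, it still counts as ongoing on Day 43, so the loss is 0% under every pattern. For AEs that ended on Days 1-42 with the end day missing, the imputed month-end reaches Day 43 in 5,373 / (365×42) = 5,373 / 15,330 = 35%.

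**5. Missing month only.** Enumerating all date pairs, the imputed date precedes first dose in 38% of cases (onset Days 1-84) or 34% (Days 1-168). It is impossible in about 1%. For example, with first dose on 20 March, an AE on the 5th of an unknown month becomes 5 March. With first dose in February, a known day of 30 has no valid date. SAP 4.2.1.1 requires a treatment-emergent AE to start on or after first dose, so a date before it could remove the AE from those tables.

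**The case against.** The strongest reply is that little is lost and that the plan already offers a second view. Much of this stands.

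- A reader might infer that all the tables answering safety objective 2 are undercounted. They are not: the occurring-or-ongoing definition is pre-specified and loses no post-switch AE. Its limits are that it mixes in pre-switch onsets, so it cannot isolate new ones, and that it can include resolved AEs.
- A reader might infer that the Week 7 window is nearly emptied. For day-missing dates, entries match exits when onset is even.
- A reader might infer that the Week 7 withdrawal question itself is compromised. Other Objective 12 (SAP 3.3) concerns withdrawal symptoms, and the MNWS is given weekly through Week 7 (protocol Appendix 5). Only the additional AE window depends on AE start dates.
- Partial dates may be few. Onset date and time are recorded (protocol 14.2), AEs are assessed weekly during treatment (protocol 14), and incomplete CRFs are queried (protocol 19.2). An AE lacking both month and day is hard to picture under weekly visits, and a known day and year with an unknown month is likely to be rare.
- The rule ignores arm, and SAP 11 plans no safety tests. A common loss fraction shrinks the absolute B-C difference by that fraction and leaves the ratio unchanged.

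What remains is the one-way direction in the start-date-only tables. Because the loss is largest just after the switch, it would not be the same in both arms if Arm B had an early cluster of onsets. The conflict inside the missing-month rule also remains, however rare the pattern.

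**Conclusion.** The concern holds in limited form and is minor. Followed exactly, SAP 6.4.1 biases the start-date-only after-Week-6 overview and the onset-period table in one known direction, blurs the Week 7 AE window, and can inflate the ongoing component of the second definition. The sizes rest on even onset and on an assumed 5-10% of AEs lacking the day. The true share is not in the documents, so an actual undercount cannot be asserted. The documents do not support reading this as a general undercount of the after-Week-6 safety tables or as a threat to Other Objective 12. The missing-month rule is wrong as written whatever its frequency, since it contradicts the sentence that governs it.

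**What to change.** - Keep the earliest-date rule for the treatment-emergent flag.
- Report by arm the number of AEs with partial start or end dates.
- Repeat the start-date-only after-Week-6 overview, the onset-period table and the Week 7 window with the latest possible start date. Repeat the ongoing table with the earliest possible end date.
- Alternatively, bound imputed dates by the visit at which the AE was first reported or recorded as resolved, if the database holds it. Protocol 14.2 does not list the reporting visit among the recorded AE fields, so check this first.
- Replace the missing-month rule with the first valid calendar date that has the known day and year and is on or after first dose.

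The cost is SAP wording, programming and a few extra descriptive tables. The repeats with opposite imputation need no new data.

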6.4.2. Questionnaire Scoring

This section describes scoring for the questionnaires that will be used in the study. No imputation will be done for missing item responses on the questionnaires. Total scores will only be computed if there are no missing item scores.

Fagerstrom Test of Nicotine Dependence (FTND)

The FTND is a 6-item multiple-choice questionnaire (see Appendix 2 of the study protocol). It will be administered at SV1. An FTND total score will be derived for each subject providing all questions have been answered, using the scoring key that follows:

Item #	Item Text	Item Response	Item Score
1	How soon after you wake up do you smoke your first cigarette?	Within 5 minutes	3
		6–30 minutes	2
		31–60 minutes	1
		After 60 minutes	0
2	Do you find it difficult to refrain from smoking in places where it is forbidden (eg, in church, at the library, in the cinema, etc.)?	Yes	1
		No	0
3	Which cigarette would you hate most to give up?	The first one in the morning	1
		All others	0
4	How many cigarettes/day do you smoke?	10 or less	0
		11 – 20	1
		21 – 30	2
		31 or more	3
5	Do you smoke more frequently during the first hours after waking than during the rest of the day?	Yes	1
		No	0
6	Do you smoke if you are so ill that you are in bed most of the day?	Yes	1
		No	0

Smoking Self-efficacy Questionnaire (SEQ-12)

The SEQ-12 is a 12-item questionnaire that will be administered at the Day 0 visit. Item scores will be assigned using the scoring key pre-printed on the questionnaire (see Appendix 3 of the study protocol). Three scores will be derived for each subject providing there are no missing questions: SEQ-12 internal stimuli score (items 1-6), external stimuli score (items 7-12) and a total score (items 1-12).

Hospital Anxiety and Depression (HADS)

The HADS questionnaire will be administered at SV1, Week 6 and Week 12. Item scores will be assigned using the scoring key pre-printed on the questionnaire (see Appendix 6 of the study protocol). Providing there are no missing questions, total scores for depression and anxiety and overall will be derived for each subject.

Brief Questionnaire of Smoking Urges (QSU-Brief)

The QSU-Brief is a 10-item questionnaire that will be administered Day 0, and at various visits during the treatment period (Day 2, Week 1 through Week 6). Item scores will be assigned using the scoring key pre-printed on the questionnaire (see Appendix 4 of the study protocol). A total QSU-Brief score will be derived for each subject, providing all questions have been answered.

Minnesota Withdrawal Scale (MNWS)

The MNWS is a 9-item questionnaire that will be administered at Day 0, and at various visits during the treatment period (Week 1 through Week 7). Item scores will be assigned using the scoring key pre-printed on the questionnaire (see Appendix 5 of the study protocol). A total MNWS score will be derived for each subject, providing all questions have been answered.

Columbia Suicide Severity Rating Scale (C-SSRS)

The C-SSRS (see Appendix 1 of the study protocol) is an assessment of both suicidal ideation and behavior. Suicidal ideation or risk for suicide (“Yes” to either question 4 or question 5 OR “Yes” to any suicidal behavior question on the C-SSRS) is an exclusion criterion.

The “Screening” version of the C-SSRS assesses suicidal ideation over the past 3 months, and suicidal behavior over the subject’s lifetime. The “Screening” version of the C-SSRS will be administered at SV1. The “Since Last Visit” version of the C-SSRS evaluates both suicidal ideation and behavior since the last assessment. This version of the C-SSRS will be administered at Week 6 and Week 12.

C-SSRS Suicidal Ideation: In both the “Screening” and “Since Last Visit” forms, there are 5 items that assess suicidal ideation. Subjects indicate (Yes/No) whether each of the following applies:

1. Wish to be dead
2. Non-specific active suicidal thoughts
3. Active suicidal ideation with any methods, without intent to act
4. Active suicidal ideation with some intent to act, without specific plan

5. Active suicidal ideation with specific plan and intent.

Each item will be assigned a numeric score (0=No, 1=Yes).

C-SSRS Suicidal Behavior: In both the “Screening” and “Since Last Visit” forms, there are 5 items that assess suicidal behavior. Subjects indicate (Yes/No) whether each of the following applies:

1. Actual attempt (non-fatal)
2. Interrupted attempt
3. Aborted attempt
4. Preparatory acts or behavior
5. Suicidal behavior

Each item will be assigned a numeric score (0=No, 1=Yes).

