APPENDIX 6. HOSPITAL ANXIETY AND DEPRESSION SCALE (HADS)

The HADS questionnaire²⁸ has been validated as a self-report instrument to measure levels of anxiety and depression and will be administered to study subjects. This questionnaire must be completed by all potential study subjects (completed = each of the 14 questions must be answered by the subject) during screening. The HADS questionnaire must be reviewed by clinic staff and a summation score calculated by totalling the numbers circled for each question at Screening Visit #1. A score ≥ 11 (**total of Depression “D” Questions only**) indicates current symptoms of moderate to severe depression and will be considered exclusionary for this study. The HADS questionnaire is to also be completed at Day 42 (Week 6) and again at Day 86 (Week 12). Analysis of results is outlined in the study Statistical Analysis Plan.

A	I feel tense or 'wound up':
3	Most of the time
2	A lot of the time
1	From time to time, occasionally
0	Not at all
D	I still enjoy the things I used to enjoy:
0	Definitely as much
1	Not quite so much
2	Only a little
3	Hardly at all
A	I get a sort of frightened feeling as if something awful is about to happen:
3	Very definitely and quite badly
2	Yes, but not too badly
1	A little, but it doesn't worry me
0	Not at all
D	I can laugh and see the funny side of things:
0	As much as I always could
1	Not quite so much now
2	Definitely not so much now
3	Not at all
A	Worrying thoughts go through my mind:
3	A great deal of the time
2	A lot of the time
1	From time to time, but not too often
0	Only occasionally
D	I feel cheerful:
3	Not at all
2	Not often
1	Sometimes
0	Most of the time

D	I feel as if I am slowed down:
3	Nearly all the time
2	Very often
1	Sometimes
0	Not at all
A	I get a sort of frightened feeling like 'butterflies' in the stomach:
0	Not at all
1	Occasionally
2	Quite Often
3	Very Often
D	I have lost interest in my appearance:
3	Definitely
2	I don't take as much care as I should
1	I may not take quite as much care
0	I take just as much care as ever
A	I feel restless as I have to be on the move:
3	Very much indeed
2	Quite a lot
1	Not very much
0	Not at all
D	I look forward with enjoyment to things:
0	As much as I ever did
1	Rather less than I used to
2	Definitely less than I used to
3	Hardly at all
A	I get sudden feelings of panic:
3	Very often indeed
2	Quite often
1	Not very often
0	Not at all

A	I can sit at ease and feel relaxed:
0	Definitely
1	Usually
2	Not Often
3	Not at all

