4.2.1.3. Other Adverse Events of Special Interest

The following events will be reported as “other adverse events of special interest”:

- Treatment-emergent suicidal ideation or risk, as measured by responses on the C-SSRS on or after first dose of study drug. Suicidal ideation or risk will be defined as a response of “Yes” to either question 4 or question 5 or “Yes” to any suicidal behavior question on the C-SSRS.

Note: Suicidal ideation or risk for suicide prior to randomization (“Yes” to either question 4 or question 5 OR “Yes” to any suicidal behavior question on the C-SSRS) is an exclusion criterion.

- Treatment-emergent moderate to severe depression, as measured by a HADS depression score ≥ 11 on or after first dose of study drug.

Note: Current symptoms of moderate to severe depression prior to randomization (HADS depression score ≥ 11) is an exclusion criterion.

- New pregnancy documented by a positive pregnancy test on or after first dose of study drug.

Note: Pregnancy is an exclusion criterion.

- Treatment-emergent coronavirus disease 2019 (COVID-19) will be selected using the Medical Dictionary for Regulatory Activities (MedDRA) standardized MedDRA query (SMQ) for COVID-19.

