11.1.2. Other Adverse Events of Special Interest

Other adverse events of special interest were defined in Section 4.2.1.3 as the following events:

- treatment-emergent suicidal ideation or behavior
- treatment-emergent moderate to severe depression
- new pregnancy
- COVID-19

The number (%) of subjects with each event will be summarized by treatment arm.

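### SAP 6.4.2 derives no HADS depression score when a depression item is blank, so a form already at 11 or more is left out of the depression event count

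*SAP*

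**What the plan says.** SAP 6.4.2 sets two general rules for all questionnaires: "No imputation will be done for missing item responses on the questionnaires", and "Total scores will only be computed if there are no missing item scores". For the HADS it adds: "Providing there are no missing questions, total scores for depression and anxiety and overall will be derived for each subject".

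SAP 4.2.1.3 defines one of its events of special interest as "Treatment-emergent moderate to severe depression, as measured by a HADS depression score ≥ 11 on or after first dose of study drug", and gives no other route to that event. SAP 11.1.2 then says: "The number (%) of subjects with each event will be summarized by treatment arm".

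Protocol Appendix 6 shows 14 items, seven for anxiety and seven for depression, each scored 0 to 3. The cut-off of 11 uses the depression items only. Appendix 6 describes the form as "completed = each of the 14 questions must be answered by the subject) during screening". It then calls for the form again at Week 6 and Week 12, the only post-baseline HADS assessments, without restating the 14-answer requirement.

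**The concern.** Declining to score an incomplete form is a common choice for a mean. It works less well for a threshold, because a partial sum can settle the classification before every item is answered. Once the answered depression items reach 11, no answer to a blank item can bring the total back below 11. Treating such a form as unscored discards a positive result that is already known.

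What is at stake is the numerator of one safety category. The neighboring suicidality event in SAP 4.2.1.3 is triggered by any qualifying positive answer on the C-SSRS, with no condition that the form be complete. Protocol Appendix 1 also requires a positive Week 6 or Week 12 C-SSRS to be reported as an adverse event. Appendix 6 has no matching instruction for a post-baseline HADS score, so the derived score is the only stated route that guarantees a positive form is counted.

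**Working it through.** The plan states no figure on this point, so there is none to reproduce. The check has three steps.

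**1. When is the classification already fixed?** Inputs from Protocol Appendix 6: seven depression items, each 0 to 3; cut-off 11. Let S be the sum of the answered depression items and m the number blank. The true total lies between S and S + 3m.

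- Event certain: S ≥ 11.
- Event excluded: S + 3m ≤ 10.
- Otherwise not determinable.

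With m = 1, a six-item sum of 11 to 18 is a certain event (true total between 11 and 21), a sum of 7 or less is never one (7 + 3 = 10), and only 8 to 10 is open. A true total of 14 or more always remains identifiable with one item blank, since 14 − 3 = 11.

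Certainty needs at least four answered depression items, since three give at most 9. Enumerating all response patterns, the sum is already 11 or more in 5 of 256 patterns with four items answered, 121 of 1,024 with five, and 1,212 of 4,096 with six. These counts show that the case can arise. They are not probabilities for real subjects. Every such pattern completes to 11 or more, so counting it needs no imputation and cannot create a false positive.

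**2. What does the SAP do with these forms?** Under 6.4.2 a form with a blank depression item has no depression score. Under 4.2.1.3 a form with no score cannot meet the definition. Under 11.1.2 it therefore adds nothing to the count. If 6.4.2 is read as applying to the whole form, a blank anxiety item has the same effect even when all seven depression items are answered.

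**3. How often might a form go unscored?** The documents give no item non-response rate. The table assumes each item is blank independently with probability q.

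| q | Any of 14 items blank, 1 − (1 − q)^14 | Any of 7 depression items blank, 1 − (1 − q)^7 | Depression items complete, an anxiety item blank, (1 − q)^7 × [1 − (1 − q)^7] |
|---|---|---|---|
| 0.2% | 2.8% | 1.4% | 1.4% |
| 0.5% | 6.8% | 3.4% | 3.3% |
| 1% | 13.1% | 6.8% | 6.3% |
| 2% | 24.6% | 13.2% | 11.4% |

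These are unscored forms, not lost events. To reach events, assume further that 1% to 5% of forms truly reach 11, independently of blanks, with 250 subjects per arm. Affected forms per arm per visit are then:

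- whole-form reading: from 250 × 0.01 × 0.028 = 0.07 to 250 × 0.05 × 0.246 = 3.1. At q = 1% the upper figure is 250 × 0.05 × 0.131 = 1.6;
- depression items only: from 250 × 0.01 × 0.014 = 0.035 to 250 × 0.05 × 0.132 = 1.65.

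Some of these forms would be not determinable rather than certain events, so the recoverable number is lower.

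**The case against.** The strongest reply is that this is a consistent, prespecified rule that ignores treatment arm and is likely to touch very few forms. Several parts of that reply stand.

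- **Display of unscored subjects.** A reader might infer that they are tabulated as having no event. The documents point elsewhere: SAP 6.2 divides by subjects with a non-missing value, and SAP 6.4 provides a missing category where applicable. They may be shown as missing or leave the denominator. The certain event is still absent from the numerator.
- **Completeness after screening.** A reader might infer that completeness is controlled only at screening. Appendix 6 and the visit descriptions in Protocol 12.2.3 call for the form to be completed at both later visits, and Protocol 19.2 requires missing data to be explained and incomplete CRFs to be queried. Blanks become less likely, but nothing says how to score one that remains.
- **The anxiety-item case.** The condition in 6.4.2 can be read score by score, and Protocol 12.2.1 treats depression as its own total. On that reading a blank anxiety item does no harm. A blank depression item still does.
- **Subjects versus assessments.** A subject with one incomplete form is still counted if the other visit's form is complete and reaches 11.
- **Other safety reporting.** SAP 11 plans no statistical comparisons for safety, and depression reported as an adverse event still enters the treatment-emergent tables in 11.1. It would not enter this HADS-defined category.

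The same criticism might seem to apply to the SEQ-12 ("Three scores will be derived for each subject providing there are no missing questions"). It does not: that questionnaire is given only at Day 0, has no threshold, and is only summarized at baseline.

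**Conclusion.** The point holds in a narrow form. SAP 6.4.2, 4.2.1.3 and 11.1.2 together leave out of the event count a Week 6 or Week 12 form that is certain to meet the cut-off. This is so on either reading of 6.4.2 when a depression item is blank, and on the literal whole-form reading when only an anxiety item is blank.

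The size is unknown and probably small. The non-response rates, their independence, and the share of forms reaching 11 are all assumptions; subjects at 11 or more at screening are excluded from entry. A reader might infer from the 2.8% to 24.6% of unscored forms that a similar share of depression events is lost in relation to randomized subjects, or that the rule favors one arm. The documents support neither: most unscored forms need not be positive, and the rule is the same in every arm. Nor do they show that distressed subjects leave more items blank. The case for change rests on a known positive going uncounted when a correct rule is simple to state.

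**What to change.** In SAP 6.4.2, derive the HADS depression score whenever its own seven items are complete, and likewise the anxiety score; keep the overall score for complete forms.

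In SAP 4.2.1.3, classify each post-baseline assessment as follows:

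- event, if the answered depression items sum to 11 or more, whatever is blank;
- no event, if the answered sum plus 3 for each blank depression item is 10 or less;
- not determinable, otherwise.

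In the SAP 11.1.2 table, show the missing or not-determinable remainder by arm. SEQ-12 scoring needs no change.

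The cost is a few sentences and minor programming. No new data are needed and no primary or secondary efficacy analysis changes. The depression event count may rise slightly.
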